9.1.1 Study calendar for capecitabine

For complete details, please see the general study calendar (Table 4).

Table 7Capecitabine study calendar

Trial Period:	Screening	Treatment Weeks									End of Treatment Post-Treatment					
	Phase	-	Capecitabine 1000 mg/m ² D1-14 every 21 days							 (last dose) or Discontinuation 						
			Cycle 1			Cycle 2			Cycle 3		Discontinuation					
Treatment Week:		1	2	3	4	5	6	7	8	9		Safety Follow-Up (30	Follow-Up Visits	Survival Follow-Up		
Scheduling Window (Days):	-28 to -1	$\pm 3d$			$\pm 3d$			$\pm 3d$				days from last dose)	(Q8W)	(Phone)		
Informed Consent	Х															
Inclusion/Exclusion Criteria	Х															
Demographics and Medical History	Х															
Prior and Concomitant Medication Review	Х	Х			Х			X then every 21 days			Х	Х				
Review Adverse Events	Х				Х			X then every 21 days			Х	Х				
12-Lead ECG	Х															
Physical Examination	Х	Х			X			X then every 21 days			Х					
Ht (V1 only), Wt, & Vital Signs (T/P/RR/BP)	Х	Х			Х			X then every 21 days			Х					
ECOG Performance Status	Х	Х			Х			X then every 21 days			Х					
Dispense capecitabine		Х			Х			X then every 21 days								
Post-Study Anticancer Therapy Status													Х	Q12W		
Survival Status														Q12W		
Pregnancy Test – Urine or Serum β HCG	Х															
PT/INR and aPTT ^e	Х															
CBC with Differential	Х	X			Х			X then every 21 days			Х					
Comprehensive Metabolic Panel	Х	Х			Х			X then every 21 days			Х					
HBV, HCV, HIV	Х															
Tumor Imaging	Х								X then every 8 weeks		Х					
CA 19-9 and CEA	Х	X			X			X then every 21 days			Х					
Newly Obtained Tissue Collection	Х					X					X					
Pharmacokinetics (Blood Collection)		•	•		Details are de	escribed in Se	ection 4.8		-	•						
Correlative Studies (Blood Collection)		Х			Х				Х		Х					

9.1.2 Study calendar for imatinib

For complete details, please see the general study calendar (Table 4).

Table 8Imatinib study calendar

Trial Period:	Screening Phase					Treatment Weeks ^a			End of Treatment	Post-Treatment			
	Thase			1	In	natinib 400 mg dail	ly	T	Discontinuation		1	r	
Treatment Week:		1	2	3	4	5	6	7	8		Safety Follow-Up (30	Follow-Up Visits ^b	Survival Follow-Up
Scheduling Window											days from last dose)	(Q8W)	(Phone)
(Days):	-28 to -1	$\pm 3d$				$\pm 3d$							
Informed Consent	Х												
Inclusion/Exclusion Criteria	Х												
Demographics and Medical History	Х												
Prior and	Х	Х		Х		X then every				Х	Х		
Concomitant Medication Review						28 days							
Review Adverse	Х			Х		X then every				Х	Х		
Events	37		-			28 days							
12-Lead ECG	X	v		v		V than arrange				v			
Examination	Λ	л		л		28 days				A			
Ht (V1 only), Wt, &	Х	Х		Х		X then every				Х			
Vital Signs (T/P/RR/BP)						28 days							
ECOG Performance	Х	Х		Х		X then every				Х			
Status						28 days							
Dispense imatinib		Х				X then every 28 days							
Post-Study												v	01200
Status												А	Q12w
Survival Status													Q12W
Pregnancy Test – Urine or Serum β	Х												
HCG													
PT/INR and aPTT ^e	Х												
CBC with Differential	Х	Х		Х		X then every				Х			
Comprehensive	Х	X		х		X then every				Х			
Metabolic Panel						28 days							
HBV, HCV, HIV	Х				•								
Tumor Imaging	Х								X then every 8 weeks	X ⁱ			
Tumor markers (CA 19-9 and CEA)	Х	Х		Х		X then every 28 days				Х			
Newly Obtained Tissue Collection	Х					X				Х			
Pharmacokinetics (Blood Collection)					Details a	are described in Sec	tion 4.8						
Correlative Studies (Blood Collection)		Х				X				Х			

9.1.3 Study calendar for ruxolitinib

For complete details, please see the general study calendar (Table 4).

Table 9Ruxolitinib study calendar

Trial Period:	Screening					Treatment	Weeks		End of Treatment	Post-Treatment				
	Phase		T	T		Ruxolitinib 1	5 mg BID	n	Discontinuation					
Treatment Week:		1	2	2	4	5	6	7	•	0		Safaty Follow Up (30	Follow Un Visits	Survival Fallow Un
Scheduling		1	2	5	4		U	/	0	,	-	days from last dose)	(O8W)	(Phone)
Window (Days):	-28 to -1	$\pm 3d$			± 3d			± 3d				2 ,		× ,
Informed Consent	Х													
Inclusion/Exclusion Criteria	Х													
Demographics and Medical History	X													
Prior and Concomitant Medication Review	Х	Х		Х		Х				X then every 4 weeks	Х	Х		
Review Adverse Events	Х			Х		Х				X then every 4 weeks	Х	Х		
12-Lead ECG and echocardiogram	Х													
Physical Examination	Х	Х		Х		Х				X then every 4 weeks	Х			
Ht (V1 only), Wt, & Vital Signs (T/P/RR/BP)	X	Х		х		Х				X then every 4 weeks	Х			
ECOG Performance Status	Х	Х		Х		Х				X then every 4 weeks	Х			
Dispense ruxolitinib		Х				Х				X then every 4 weeks				
Post-Study Anticancer Therapy Status													х	Q12W
Survival Status														Q12W
Pregnancy Test – Urine or Serum β HCG	Х													
PT/INR and aPTT	Х													
CBC with Differential	X	Х		Х		Х		X		X then every 2 weeks	X			
Comprehensive Metabolic Panel	X	Х		Х		X					X			
HBV, HCV, HIV	X													
Lipid panel	X									X then every 9 weeks				
Tumor Imaging	Х										Х			
Tumor markers (CA 19-9 and CEA)	X	Х		Х		Х				X then every 4 weeks	X			
Newly Obtained Tissue Collection	X					Х					X			
Pharmacokinetics (Blood Collection)		Details are described in Section 4.8												
Correlative Studies (Blood Collection)		Х				Х					Х			

9.2 Trial Procedures

The Trial Flow Chart (Section 9) summarizes the trial procedures to be performed at each visit. Individual trial procedures are described in detail below. It may be necessary to perform these procedures at unscheduled time points if deemed clinically necessary by the investigator. Furthermore, additional evaluations/testing may be deemed necessary by the Sponsor for reasons related to safety. In some cases, such evaluation/testing may be potentially sensitive in nature (e.g. HIV, Hepatitis C, etc.), and thus local regulations may require that additional informed consent be obtained from the subject. In these cases, such evaluations/testing will be performed in accordance with those regulations.

9.3 Administrative Procedures

9.3.1 Informed Consent

The investigator must obtain documented consent from each potential subject or each subject's legally acceptable representative prior to participating in a clinical trial.

Consent must be documented by the subject's dated signature or by the subject's legally acceptable representative's dated signature on a consent form along with the dated signature of the person conducting the consent discussion. A copy of the signed and dated consent form should be given to the subject before participation in the trial.

The initial informed consent form, any subsequent revised written informed consent form, and any written information provided to the subject must receive the IRB/ERC's approval/favorable opinion in advance of use. The subject, or his/her legally acceptable representative, should be informed in a timely manner if new information becomes available that may be relevant to the subject's willingness to continue participation in the trial. The communication of this information will be provided and documented via a revised consent form or addendum to the original consent form that captures the subject's dated signature or by the subject's legally acceptable representative's dated signature.

The informed consent will adhere to IRB/ERC requirements, applicable to state laws, and federal regulations.

9.3.2 Inclusion/Exclusion Criteria

All inclusion and exclusion criteria will be reviewed by the investigator or qualified designee to ensure that the subject qualifies for the trial (see Section 5).

9.3.3 Medical History

A medical history will be obtained by the investigator or qualified designee. Medical history will include all active conditions and any condition diagnosed within the prior 10 years that is considered to be clinically significant by the investigator. Details regarding the disease for which the subject has enrolled in this study will be recorded separately and not listed as medical history.

9.3.4 Prior and Concomitant Medications

Concomitant therapy includes any medication (e.g. prescription drugs, over-the-counter drugs, herbal or homeopathic remedies, nutritional supplements) used by a patient from 7 days prior to screening to the treatment discontinuation visit. All such medications should be reported to the investigator and recorded to the Concomitant Medications Case Report Form (CRF). All medications related to reportable SAEs and ECIs should be recorded.

9.3.5 Disease Details and Treatments

The investigator or qualified designee will obtain prior and current details regarding disease status.

Prior Treatment Details: The investigator or qualified designee will review all prior cancer treatments including systemic treatments, radiation, and surgeries.

Subsequent Anti-Cancer Therapy Status: The investigator or qualified designee will review all new anti-neoplastic therapy initiated after the last dose of trial treatment. If a subject initiates a new anti-cancer therapy within 30 days after the last dose of trial treatment, the 30-day Safety Follow-Up visit must occur before the first dose of the new therapy. Once new anti-cancer therapy has been initiated, the subject will move into survival follow-up.

9.3.6 Long-Term Follow Up

After completion of the posttreatment safety visit, subjects will be followed for disease and survival status by telephone contact or other method every three months for one year from treatment discontinuation, then every six months thereafter. Long-term follow-up will continue until the subject has withdrawn consent for further participation, is lost to follow-up, has died, or the Sponsor makes a decision to close the study.

9.4 Clinical Procedures and Assessments

9.4.1 Adverse Event (AE) Monitoring

The investigator or qualified designee will assess each subject to evaluate for potential new or worsening AEs as specified in the Trial Flow Chart (Section 9) and more frequently if clinically indicated. AEs will be graded and recorded throughout the study and during the follow-up period according to NCI CTCAE Version 4.0 (Appendix B). Toxicities will be characterized in terms regarding seriousness, causality, toxicity grading, and action taken with regard to trial treatment.

Refer to Section 8 for detailed information regarding the assessment and recording of AEs.

9.4.2 Physical Exam

The investigator or qualified designee will perform a complete physical exam during the screening period. Clinically significant abnormal findings should be recorded as medical history. A physical exam should be performed as specified in the Trial Flow Chart (Section 9). For subsequent cycles, the investigator or qualified designee will perform a directed physical exam as clinically indicated prior to dosing on Day 1 of each treatment cycle. After

the first dose of trial treatment, new clinically significant abnormal findings should be recorded as AEs.

9.4.3 Vital Signs

The investigator or qualified designee will take vital signs at screening, prior to the administration of each dose of trial treatment, and at treatment discontinuation as specified in the Trial Flow Chart (Section 9). Vital signs should include temperature, pulse, respiratory rate, weight, and blood pressure. Height will be measured at screening only.

9.4.4 Eastern Cooperative Oncology Group (ECOG) Performance Status

The investigator or qualified designee will assess ECOG status (Appendix A) at screening, prior to the administration of each dose of trial treatment, and at discontinuation of trial treatment as specified in the Trial Flow Chart (Section 9).

9.4.5 Tumor Imaging and Assessment of Disease

CT chest, abdomen, and pelvis with contrast will be performed at baseline screening, prior to the administration of study drugs, and every 8 weeks thereafter. Subjects will be evaluated for diease response and progression according to RECIST v1.1. Disease status categories include complete response (CR), partial response (PR), stable disease (SD), and progression of disease (PD).

9.4.6 Tumor Tissue Collection, Pharmacokinetics, & Correlative Studies Blood Sampling All patients will have tumor biopsy specimens obtained at baseline prior to study drug administration and then at week 4 (optional) to assess for successful collapse of the master regulator signature in a given patient's tumor. A biopsy will also be requested (optional) at the time of disease progression. Tissue collection, handling, processing, and storage instructions are described in the separate study manual.

Peripheral blood will be collected for pharmacokinetic analysis only during Cycle 1. The timing of blood sampling will vary by study drug (Section 4.8). The exact times of medication administration and the times of these blood samples must be recorded on the appropriate CRF. A validated assay will be used to measure plasma drug concentration. Blood processing, handling, and storage instructions are described in Section 4.8 as well as in the separate study manual.

Peripheral blood will be collected pre-treatment, cycle 1 day 1, and cycle 2 for future evaluation of biomarkers. The analyses may include genomics, transcriptomics, and proteomics. Assessment of ctDNA and OncoTreat analysis on circulating tumor cells (CTCs) may also be performed.

9.4.7 Laboratory Procedures/Assessments

Details regarding specific laboratory procedures/assessments to be performed in this trial are provided below. Laboratory tests for hematology, chemistry, urinalysis, and others are specified in the Trial Flow Chart (Section 9).

Laboratory tests for screening should be performed within 7 days prior to the first dose of study treatment. After Cycle 1, pre-dose laboratory procedures can be conducted up to 72 hours prior to dosing. Results must be reviewed by the investigator or qualified designee and found to be acceptable prior to each dose of trial treatment.

10. MEASUREMENT OF EFFECT

10.1 Antitumor Effect – Solid Tumors

For the purposes of this study, patients should be re-evaluated for response every 8 weeks. In addition to a baseline scan, confirmatory scans should also be obtained 8 weeks (not less than 4) weeks following initial documentation of objective response.

Response and progression will be evaluated in this study using the new international criteria proposed by the revised Response Evaluation Criteria in Solid Tumors (RECIST) guideline (version 1.1) [Eur J Ca 45:228-247, 2009]. Changes in the largest diameter (unidimensional measurement) of the tumor lesions and the shortest diameter in the case of malignant lymph nodes are used in the RECIST criteria.

10.2 Definitions

Evaluable for toxicity: All patients will be evaluable for toxicity from the time of their first treatment with an OncoTreat-prioritized agent.

Evaluable for objective response: Only those patients who have measurable disease present at baseline, have received at least one cycle of therapy, and have had their disease re-evaluated will be considered evaluable for response. These patients will have their response classified according to the definitions stated below. (*Note*: Patients who exhibit objective disease progression prior to the end of cycle 1 will also be considered evaluable.)

Evaluable for feasibility – primary outcome: All subjects who receive a single dose of study drug will be included in the primary outcome analysis of feasibility.

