2. STUDY OBJECTIVES AND ENDPOINTS

2.1 Primary Objectives & Endpoints

2.1.1 Objectives:

The co-primary objectives of this study are:

- To evaluate the overall feasibility of using the OncoTreat technology to inform rational selection of off-label FDA-approved or investigational drugs in subjects with advanced pancreatic cancer (PDA) who have progressed on one or two prior lines of systemic therapy. This will include the percentage of subjects who begin an OncoTreat-prioritized agent, defined as having received a single dose of study drug, and the "match rate," defined as the fraction of subjects who match with at least one OncoTreat-prioritized agent (p-value < 1 x 10⁻⁵).
- To evaluate the clinical efficacy of OncoTreat by assessing the objective response rate (ORR) for subjects with advanced PDA treated with OncoTreat-prioritized drugs after disease progression on one or two prior lines of systemic therapy according to Response Evaluation Criteria in Solid Tumors (RECIST) v1.1 criteria.
- 2.1.2 Endpoints:

The co-primary endpoints of interest are:

- The percentage of subjects who begin an OncoTreat-prioritized agent, defined as having received a single dose of study drug, and the "match rate," defined as the fraction of subjects who match with at least one OncoTreat-priotitized agent (p-value $< 1 \ge 10^{-5}$).
- ORR according to RECIST v1.1 criteria.

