- b. Subjects who discontinue study treatment without documented disease progression should continue to be monitored for disease by radiologic imaging every 8 weeks (±7 days) until (1) the start of new anti-cancer treatment, (2) disease progression, (3) death, or (4) the end of the study, whichever occurs first.
- c. Informed consent will include consent for correlative studies including biopsies and serum collections.
- d. For women of reproductive potential, a negative pregnancy test should be performed within 72 hours prior to first dose of trial treatment. Pregnancy tests (serum and/or urine) should be repeated if required by local guidelines.
- e. Laboratory screening tests should be performed within 14 days prior to first dose of study treatment. For all subjects, unresolved abnormal labs resulting in drug-related AEs should be followed until resolution.
- f. All subjects will be tested for HIV, HBV, and HCV prior to enrollment. Those who are positive for HIV, untreated active Hepatitis B, and dual infection with HBV/HCV will be excluded.
- g. Tumor imaging at screening: Imaging will be performed within 28 days prior to the first dose of OncoTreat-prioritized drug. Imaging should include CT chest, abdomen, and pelvis or MRI if CT is clinically contraindicated.
- h. The first on-study tumor imaging will be performed after 8 weeks (±7 days) of treatment and will continue every 8 weeks (±7 days) thereafter (or more frequently if clinically indicated). Timing of imaging follows calendar days and should not be adjusted due to dose interruptions. The same imaging technique, acquisition, and processing parameters for a subject should be used throughout the trial if possible.
- i. Subjects without confirmed PD who discontinue treatment will have imaging performed at the time that study treatment is discontinued (i.e. date of discontinuation ± 4 week window). If a scan was obtained within 4 weeks prior to discontinuation of treatment, then imaging at treatment discontinuation is not required. Subjects who discontinue treatment after confirmed PD will not need further imaging performed during the follow-up period.
- j. Following disease progression/intolerance to standard of care therapy, a fresh tumor biopsy (primary or metastatic site) is required to be performed after the last dose of systemic therapy. OncoTreat analysis will confirm the master regulator profile and the recommended OncoTreat-informed drug.

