10.7.1 Objective Response Rate (ORR)

ORR is defined as the proportion of the subjects in the analysis population who have a CR or PR. Responses are based on assessments per RECIST 1.1.

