12. STATISTICAL CONSIDERATIONS

This is a single arm, phase Ib study with 2 co-primary endpoints:

- Feasibility: The primary objective of this trial is to determine the feasibility of the OncoTreat platform in guiding therapy. The primary outcome is whether a subject begins therapy on Part 2. Previous attempts to match subjects based on DNA profiling have yielded enrollment rates of 3-5% [14, 78]. We hypothesize that we will validate OncoTreat matches for 50% of subjects and that at least 30% of enrolled subjects (60% of matches) will begin therapy on Part 2. With 30 enrolled patients on Part 1, we will have 80% power to detect a treatment rate of 30% on Part 2 compared to a historical treatment rate of 5% with alpha of 0.05. We will also assess the "match rate" the fraction of patients who match with at leaset one drug. With 30 enrolled subjects, we will have 97% power with alpha = 0.05 to detect a 50% match rate (15 of 30 subjects) compared to a (liberal) estimated match rate of 20% based on DNA profiling in PDA.
- Efficacy: The primary clinical efficacy endpoint is the **objective response rate (ORR)** for OncoTreat-prioritized drugs, which corresponds to the number of patients whose tumors demonstrate a 30% or greater reduction from baseline in the sum of the diameters of all target lesions amongst all evaluable patients, as assessed by standard-of-care CT scans. We target estimating the ORR and the corresponding 95% confidence interval.

Secondary endpoints will include: 1) **disease control rate (DCR) at 16 and 24 weeks**, which corresponds to the number of patients whose tumors demonstrate either an objective response or stable disease, defined as a no more than 20% increase from baseline in the sum of the diameters of all target lesions; 2) **median progression-free survival (mPFS)**, defined as the median duration prior to the development of disease progression or patient death; 3) **overall survival (OS)**, defined as time from first dose of OncoType-informed drug to death due to any cause; and 4) **safety and tolerability**, defined as the incidence of Grade 3/4 AEs in terms categorized and graded according to NCI CTCAE v4.0. We will estimate DCR, mPFS, and OS and their 95% confidence interval.

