The phase III trial (NAPOLI-1) that resulted in the FDA-approval of nanoliposomal irinotecan and 5-fluorouracil in the second-line setting demonstrated a median overall survival of 6.1 months versus 4.2 months for 5-fluorouracil monotherapy (primary endpoint), mPFS of 3.1 months, and an ORR of 16% (compared to 1% in the 5-fluorouracil arm) [7]. Fifty-one (12%) patients had not had previous treatment for metastatic disease, 234 (56%) had received one previous line of metastatic treatment, and 132 (32%) had previously received two or more lines of metastatic treatment. The disease control rate was less than 20% and did not differ between treatment groups. Thus, based on historical controls, the ORR for treatment-resistant metastatic PDAC is expected to be no more than 16%.

Using the above mentioned rates, a sample size of n = 9 achieves at least a 80% power to detect a difference of 25% in ORR (30% vs 5%) using a one-sided binomial test with a target alpha of 0.1. To be conservative, we use the minimum number of patients (9) expected to be treated in this calculation. If at the end of the study the total number of objective responses is greater than or equal to 2, we will be able to reject the historical rate of 5% at the significance level of 0.05 with power of 69% and OncoTreat will have demonstrated a clear signal of clinically meaningful improvement in the primary endpoint for patients with advanced, previously-treated PDA. Assuming about 30% of enrolled patients will receive an OncoTreat-informed treatment, N = 30 subjects is an appropriate sample size for this prospective study.

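### The co-primary ORR leaves out treated patients who die or stop early without a repeat scan or a full cycle, so the estimate and its 95% CI can be too high

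*Combined protocol and SAP*

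**What the plan says.** The co-primary efficacy objective in Section 2.1.1 is the ORR "for subjects with advanced PDA treated with OncoTreat-prioritized drugs". The sample-size paragraph in Section 12 uses the same population: "we use the minimum number of patients (9) expected to be treated in this calculation". Its success rule is a count, namely that "the total number of objective responses is greater than or equal to 2".

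The analysis uses a different population. Section 12 defines the ORR through patients whose tumors "demonstrate a 30% or greater reduction from baseline in the sum of the diameters of all target lesions amongst all evaluable patients", and says the aim is to estimate the ORR with a 95% confidence interval. Section 10.2 limits evaluability to patients with measurable baseline disease who "have received at least one cycle of therapy, and have had their disease re-evaluated will be considered evaluable for response". A note there keeps patients with objective progression before the end of cycle 1. Section 10.7.1 says "ORR is defined as the proportion of the subjects in the analysis population who have a CR or PR", without stating what that population is.

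On imaging, the first on-study scan is at 8 weeks (±7 days). Footnote i to the study calendar (Section 9.1) adds that "Subjects without confirmed PD who discontinue treatment will have imaging performed at the time that study treatment is discontinued", but also that "If a scan was obtained within 4 weeks prior to discontinuation of treatment, then imaging at treatment discontinuation is not required". Footnote b continues scans every 8 weeks after stopping without progression. Section 10.5.3 gives clinical deterioration without objective progression its own label and asks for every effort to document progression afterwards. It does not say how such a patient enters the ORR. Section 4.2 allows no replacement of subjects.

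**The concern.** The objective and the sample size concern treated patients, while the analysis concerns a subset selected after treatment starts. Membership of that subset depends on surviving and staying on drug long enough to complete a cycle and be scanned, which is related to outcome. Three kinds of treated patient leave the denominator:

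- those who die before a repeat scan;
- those who deteriorate or withdraw and are not scanned again;
- those who stop during cycle 1 without objective progression, for example for toxicity, even if they are scanned later.

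No section counts them as non-responders, and no all-treated ORR is planned, even as a sensitivity analysis. Early loss is plausible. Patients have progressed on, or not tolerated, one or two prior lines, and Section 3.1 cites median PFS of 3.1 and 1.5 months in the second-line reference trial. What is at stake is the accuracy of the reported ORR and its confidence interval.

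A second inconsistency sits in the same sentence of Section 12. It describes response as a target-lesion reduction of at least 30%. Sections 2.1.2, 10.5.3 and 10.7.1 use RECIST 1.1, and 10.5.3 takes account of new lesions, non-target progression and confirmation. Read literally, the Section 12 wording could add responders and so affect the count rule.

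**Working it through.** **Inputs.** From Section 12: n = 9, null ORR 5%, alternative 30%, one-sided binomial test, target alpha 0.1, at least 2 responses. From the synopsis: an estimated 15 subjects progressing to Part 2. The number of non-evaluable patients is not given, so the drop-outs below are assumptions.

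**The plan's own figure.** With X binomial on 9 patients:

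- alpha = 1 − 0.95⁹ − 9(0.05)(0.95⁸) = 1 − 0.6302 − 0.2985 = 0.0712, within the 0.1 target;
- power at 30% = 1 − 0.7⁹ − 9(0.3)(0.7⁸) = 1 − 0.0404 − 0.1556 = 0.804.

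The stated power of at least 80% reproduces with all 9 treated patients in the denominator. Section 12 also attaches a level of 0.05 and 69% power to the same rule. Those figures do not reproduce at n = 9, but that is a separate matter.

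**Size of the inflation.** If a fraction f of treated patients is dropped and all are non-responders, the ORR is multiplied by 1/(1 − f). For 1, 2 or 3 of 9 dropped this is 9/8 = 1.125, 9/7 = 1.286 or 9/6 = 1.5.

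**Estimates.** For x responders among n, the exact 95% limits are the 0.025 quantile of Beta(x, n − x + 1) and the 0.975 quantile of Beta(x + 1, n − x). The p-value is the one-sided probability of x or more responses at a true rate of 5%.

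| Treated | Dropped | Responders / n | ORR | 95% CI | p vs 5% |
|---|---|---|---|---|---|
| 9 | 0 | 2/9 | 22.2% | 2.8–60.0 | 0.071 |
| 9 | 1 | 2/8 | 25.0% | 3.2–65.1 | 0.057 |
| 9 | 2 | 2/7 | 28.6% | 3.7–71.0 | 0.044 |
| 9 | 3 | 2/6 | 33.3% | 4.3–77.7 | 0.033 |
| 15 | 0 | 2/15 | 13.3% | 1.7–40.5 | 0.171 |
| 15 | 3 | 2/12 | 16.7% | 2.1–48.4 | 0.118 |
| 15 | 4 | 2/11 | 18.2% | 2.3–51.8 | 0.102 |
| 15 | 0 | 3/15 | 20.0% | 4.3–48.1 | 0.036 |
| 15 | 3 | 3/12 | 25.0% | 5.5–57.2 | 0.020 |
| 15 | 4 | 3/11 | 27.3% | 6.0–61.0 | 0.015 |

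All the 9-treated p-values are below 0.1. With 2 or 3 dropped they also fall below 0.05. No 15-treated case crosses 0.05 or 0.1.

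**Do the imaging provisions close the gap?** They reduce it.

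- A discontinuation scan cannot cover a death.
- The waiver in footnote i can be met by the baseline scan, because footnote g allows baseline imaging up to 28 days before the first dose. For example, a patient scanned 10 days before the first dose who stops 14 days after it has a scan 10 + 14 = 24 days old, and no new one is required.
- For a patient who stops within cycle 1, a scan that does not show progression before the end of cycle 1 does not restore evaluability, because the one-cycle condition still fails.

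The measurable-disease condition should remove nobody, since Section 5.1 already requires it for entry.

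**The case against.** The evaluable set is pre-specified, and Sections 10.2, 10.7.1 and 12 read together do point to it. On that reading 10.7.1 lacks a cross-reference and little more. This is fair as far as it goes, but it does not reconcile the set with the treated population in the objective and the sample size.

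The practical effect may be modest. The shifted estimates lie well inside either interval, and the rule is a count. A p-value crossing 0.05 matters only if a p-value is recomputed on the evaluable number. Entry criteria (ECOG 0–1, predicted life expectancy over 3 months) should limit early loss. All of this stands, and it is why the effect is on the estimate and CI.

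The direction of bias is not guaranteed in every case. A patient who stops in cycle 1 for toxicity could later be scanned and show a response, and Section 10.2 would then remove a responder. That is possible but should be rare. The statement that the count rule is unaffected holds when the dropped patients are non-responders.

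The 15-treated case is open to challenge, because Section 12 treats 15 as the number of matches and 9 as the number starting therapy. The synopsis does estimate 15 progressing to Part 2, so the case is kept as an assumption.

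Finally, the 30% wording in Section 12 is probably shorthand for partial response. It still conflicts with the RECIST definition elsewhere and is simple to correct.

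**Conclusion.** The concern holds. As written, the co-primary ORR is estimated in a subset that leaves out treated patients likely to be non-responders, while the objective and n = 9 concern all treated patients. With 9 treated and 2 responders, dropping 1 to 3 non-responders raises the ORR from 22.2% to between 25.0% and 33.3%, and moves the 95% CI from 2.8–60.0 to between 3.2–65.1 and 4.3–77.7. With 15 treated and 3 to 4 dropped, 13.3% becomes 16.7–18.2% and 20.0% becomes 25.0–27.3%. These figures assume the number lost and assume that all those lost are non-responders. On that basis the success rule of at least 2 responses is unaffected by the denominator. The literal Section 12 response wording could affect it. The change should be made, but the design does not fail without it.

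**What to change.** In Sections 10.2, 10.7.1 and 12, define the primary ORR population as all subjects who receive at least one dose of an OncoTreat-prioritized agent. State that subjects with no post-baseline tumor assessment count as non-responders. A subject who stops early but is scanned is then classified by RECIST 1.1 on the scans obtained. Keep the Section 10.2 evaluable set as a supportive analysis reported alongside.

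In Section 12, replace the target-lesion description of response with confirmed CR or PR as best overall response per Section 10.5.3.

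The cost is wording in three sections. No extra patients, data or scans are needed, since Section 10.1 already plans confirmatory scans. The downside is a somewhat lower reported ORR.
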